Administration of study drug will occur at Week 0, 12, 24 and 36, with an additional dose of rizankizumab made available at the Week 4 visit for those subjects that have not achieved a protocol defined response (defined as an improvement in tender and swollen joint count of \geq 20% compared with the baseline in Study 1311.5), provided the investigator believes this may be beneficial to the subject. Subjects who have not attained a protocol defined response at 2 consecutive visits at Week 12 visit or thereafter, will be discontinued from the OLE study. Other criteria leading to discontinuation of individual subjects in this trial are described in Section [5.4.1](#).

A \pm 4-day window is permitted around scheduled study visits after enrollment. If any visit has to be rescheduled, subsequent visits should follow the original visit date schedule.

Follow-Up Period

Subjects will have follow-up visits at Week 48 and 52 and a Follow-up Phone call 20 weeks after the last dose of study drug. All Follow-up Visit procedures are noted in [Appendix C](#). Subjects who discontinue study drug treatment early will need to attend an early End of Treatment (EOT) visit ideally within 2 weeks after the decision and preferably prior to the administration of any new therapies. An End of Study (EOS) visit 16 weeks after the last dose of study drug and a Follow-up Phone Call 20 weeks after the last dose of study drug is required to determine the status of any ongoing AEs/SAEs or the occurrence of any new AEs/SAEs (see [Appendix C](#) and Section [5.4.1](#)).

A schematic of the study design is shown below in [Figure 2](#).

Figure 2. Study M16-244 Study Design

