a. For subjects rolling over from Study 1311.5 to the OLE (Study M16-244) with ≤ 4 day delay, these procedures do not need to be repeated. Results assessed at the Week 24 visit of Study 1311.5 will serve as V1 (Week 0) visit results for Study M16-244. Subjects initiating the OLE with a delay of > 4 days and ≤ 8 weeks from completion of Study 1311.5 Week 24 visit will need to complete all activities for V1. If a subject enrolls into the OLE (Study M16-244), participation in Study 1311.5 is completed and the early completion of the Study 1311.5 is documented (EOS). All procedures of Study 1311.5 trial at Week 24 should be completed prior to the start of the Study M16-244 trial.

b. To be completed prior to initiation of Study M16-244 procedures.

c. Transcribe medical history from Study 1311.5 and record any updates.

d. Subject to complete PROs in the order listed, before any other visit assessments or treatments and, if possible, before any interaction with the investigator or other members of the study team.

- e. A symptom directed physical exam should be performed when necessary and if needed for physician assessments/questionnaires. Complete physical examination will include vital sign assessment and general appearance as well as evaluation of all organ systems. Targeted physical examination will include vital sign assessment and evaluation of organ systems associated with AE(s) symptoms or laboratory abnormalities. Clinically relevant abnormal findings will be reported as baseline conditions or AEs.
- f. For subjects rolling over from Study 1311.5 to the OLE without any delay, concomitant medication ending prior to first dose in Study M16-244 will be recorded in preceding Study 1311.5. Medications ongoing from preceding Study 1311.5 after first dose in Study M16-244 will be recorded in Study M16-244.
- g. For subjects rolling over from Study 1311.5 to the OLE Adverse Events ending prior to completion of Study M16-244 ICF will be recorded in preceding Study 1311.5.
- h. Complete clinical assessment prior to completing Study M16-244 ICF will be recorded in the eCRFs of Study M16-244.
- i. Subjects who prematurely discontinue from the trial will not be required to collect x-rays at each designated time point, unless they received a dose within the 16 weeks prior to the scheduled time point.

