#### **4.3                   Overall Study Design and Plan**

This is a 52-week multicenter, single-arm, OLE study to assess safety, tolerability and efficacy of risankizumab in PsA subjects who have completed all doses of study drug and the Week 24 visit of Study 1311.5 (Phase 2 randomized clinical trial in PsA subjects, sponsored by Boehringer Ingelheim).

Subjects who complete all doses of study drug and the Week 24 visit in Study 1311.5, meet all inclusion criteria (Section 5.2.1 of the protocol) and none of the exclusion criteria (Section 5.2.2 of the protocol) have the option to sign the informed consent form and enter

the OLE study, receiving risankizumab 150 mg administered every 12 weeks with an additional dose of risankizumab made available at the Week 4 of the OLE study visit for those subjects that have not achieved a protocol defined response (defined as an improvement in tender and swollen joint count of  $\geq 20\%$  compared with the baseline in Study 1311.5), provided the investigator believes this may be beneficial to the subject.

[figure not shown]
If the Study M16-244 Week 0 visit occurs on the same day or in the 4 days following the Study 1311.5 Week 24 visit, only selected activities are required as some activities are common to both studies and are not required twice. See Study Activity Table in Appendix C of the protocol. If the OLE Week 0 visit occurs  $> 4$  days and  $\leq 8$  weeks after the Study 1311.5 Week 24 visit, all procedures specified in Appendix C of the protocol at Week 0 of the OLE study are required.

Subjects that enroll in the OLE study are no longer enrolled in Study 1311.5 and will not complete the Week 28 or Week 32 visits in Study 1311.5.

Subjects who are not enrolled in Study M16-244 within 8 weeks of the Study 1311.5 Week 24 visit are not eligible to participate in Study M16-244.

This study is anticipated to enroll up to 180 subjects. Study visits will occur at Week 0/Enrollment, Week 4, 12, 24, 36, 48 and 52. A  $\pm 4$  day window is permitted around scheduled study visits after enrollment.

A schematic of the study design is shown below in [Figure 1](#).

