## **6.3                   Definition of Rx Days (Days Relative to the First Dose of Study Drug)**

Rx days are calculated for each time point relative to the date of first dose of study drug. They are defined as the number of days between the date of the first dose of study drug and the specific time point. Rx days are negative values when the time point of interest is prior to the first study drug dose day. Rx days are positive values when the time point of interest is on or after the first study drug dose day. The day of the first dose of study drug is defined as Rx Day 1, while the day prior to the first study drug dose is defined as Rx Day –1 (there is no Rx Day 0).

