## **6.4                   Definition of Analysis Windows**

All time points and corresponding time windows are defined based on Rx Days.

For efficacy analyses, laboratory parameters, and vital sign variables, analysis windows are constructed using the following algorithm:

- Determine the nominal Rx day for each visit (e.g., Week 4 [4 weeks after Baseline visit] equals Rx Day 29).
- In order to include all post baseline data, the first post-baseline interval starts on the first day after the first dose of study drug (Rx Day 2).

---

- Determine the window around a specific nominal Rx day by adding or subtracting half of the interval between adjacent visits (e.g., days between Week 2 and Week 4 is 14). The threshold between adjacent visits is determined by splitting the interval evenly between the visits. If the resulting split is between Rx days, then the threshold is determined as the midpoint between the adjacent visits. If the resulting split is on a Rx day, then the threshold is determined as being between that Rx day and the Rx day prior to it (e.g., the split between Week 2 and Week 4 would be between Rx Days 22 and 23).
- If more than one assessment is included in a time window the assessment closest to the nominal day will be used. If there are two observations equidistant to the nominal day, the one after the nominal day will be used in analyses. If more than one assessment is included on the same day, then the worst assessment on that day will be used in analyses. For laboratory values, if there are multiple measurements on the same day, average value will be used.

The protocol specified visits and corresponding time windows used in the various efficacy analyses, laboratory parameters, and vital sign variables, are presented in the following tables.

**Table 1. Analysis Windows for Efficacy Variables (PtGA, Patient's Assessment of PsA Pain Intensity, HAQ-DI, SF-36v2, TJC68, SJC66, PASI, BSA, sPGA, PhGA, hsCRP for DAS)**

Protocol Specified Visit Week	Lower Bound	Target Day	Upper Bound
0	1	1	1
4	2	29	57
12	58	85	127
24	128	169	211
36	212	253	295
48	296	337	351
52	352	365	378

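### Feeder Week 24 results that stand in as Week 0 for 1–4 day rollovers fall outside the Rx Day 1 window if they keep their own dates, and leave the descriptive Week 0 rows

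*Protocol*

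**What the plan says.** **Rollover rule.** Protocol Appendix C, footnote a, covers subjects who roll over "with ≤ 4 day delay, these procedures do not need to be repeated". For them, "Results assessed at the Week 24 visit of Study 1311.5 will serve as V1 (Week 0) visit results for Study M16-244". Subjects with a longer gap, up to 8 weeks, complete all Week 0 activities. SAP 4.3 repeats the split: if the "Week 0 visit occurs on the same day or in the 4 days following the Study 1311.5 Week 24 visit, only selected activities are required".

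**First dose.** Protocol 5.1: "Administration of study drug will occur at Week 0, 12, 24 and 36". The gap to the Week 0 visit is therefore the gap to the first open-label dose.

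**Windows.** SAP 6.4: "All time points and corresponding time windows are defined based on Rx Days". SAP 6.3 makes the first-dose day Rx Day 1, has no Day 0, and adds: "Rx days are negative values when the time point of interest is prior to the first study drug dose day". The Week 0 row of Tables 1, 2, 3, 4 and 6 has lower bound 1, target 1 and upper bound 1. The next window in each table opens on Rx Day 2.

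**Missing visits.** SAP 6.5 summarizes observed data only. A subject without an evaluation at a visit is left out of that visit's summary.

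**The concern.** The protocol names a specific record as the Week 0 value for prompt rollovers, and the SAP's window cannot hold that record unless rollover and dosing fall on the same day. A pre-dose assessment 1 to 4 days old is a legitimate entry value, and nothing suggests that the SAP meant to exclude it.

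At stake is the Week 0 row of the by-visit tables. SAP 10.3 and 10.4 summarize ACR20 and most other endpoints at every measured time point in Study M16-244, and SAP 11.3.2 and 11.4.2 do so by visit for laboratory and vital-sign data. Week 0 shows status at entry to open-label treatment, and SAP 10.6 breaks the secondary endpoints down by prior randomization. If the stand-in records are lost, that row omits a set of subjects defined only by rollover timing, while later rows include them.

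**Working it through.** No power or error-rate figure is involved. The check is a date lookup.

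**Inputs.** Delays of 0–4 days without repeat procedures (Protocol Appendix C, footnote a; SAP 4.3); dose at Week 0 (Protocol 5.1); day numbering (SAP 6.3); window bounds (SAP Tables 1–4 and 6).

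**Reproducing the SAP's own figures.** Target day = 7 × week + 1. Weeks 0, 4, 12, 24, 36, 48 and 52 give 1, 29, 85, 169, 253, 337 and 365, as in Table 1. The midpoints of adjacent post-dose targets are (29 + 85)/2 = 57, (85 + 169)/2 = 127, (169 + 253)/2 = 211, (253 + 337)/2 = 295 and (337 + 365)/2 = 351. These match the upper bounds in Table 1.

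**Placing the stand-in record.** Let x = assessment date minus date of first M16-244 dose. Rx Day = x + 1 if x ≥ 0, and x if x < 0.

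| Delay (days) | x | Rx Day of feeder Week 24 result | Window in Tables 1–4 and 6 |
|---|---|---|---|
| 0 | 0 | 1 | Week 0 |
| 1 | -1 | -1 | none |
| 2 | -2 | -2 | none |
| 3 | -3 | -3 | none |
| 4 | -4 | -4 | none |
| over 4 | repeated at Week 0, x = 0 | 1 (repeat value) | Week 0 (repeat value) |

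Every variable in Tables 1–4 and 6 carries footnote a at Week 0 in Appendix C. Local tolerability (Table 7) does not, so it is unaffected.

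**Which dose anchors Rx Day.** SAP 6.3 does not name the study. Anchored to the first Study 1311.5 dose, the feeder Week 24 visit would be Rx Day 24 × 7 + 1 = 169, inside the Week 24 window (128–211) and still not Week 0. Under that anchor, and with no delay, the open-label Week 52 visit would be Rx Day (24 + 52) × 7 + 1 = 533, beyond the last bound of 378. The tables only work if anchored to the first M16-244 dose, but the text should say so.

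**Does another rule recover the record?**
- The nominal visit label does not for ACR: SAP 10.7.1 uses the derived window in place of the CRF visit label, and MDA and PsARC follow ACR logic.
- The baseline rule in SAP 6.1 looks back from the first dose in Study 1311.5, not in M16-244.
- Only mTSS (Table 5) has windows that explicitly take in feeder data.

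**Count.** The distribution of delays is not given, so the number affected could be anywhere from 0 to 180. Illustrative shares: 180 × 0.05 = 9; 180 × 0.10 = 18; 180 × 0.20 = 36.

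**Effect of the proposed window.** Rx Day -4 through 1 captures delays of 0, 1, 2, 3 and 4 days. It leaves out feeder results at Rx Day -5 or earlier, which belong to subjects who repeat Week 0.

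**The case against.** The strongest reply is that exclusion is an inference. Protocol 10.1 allows data common to both studies to be shared and promises sponsor instructions on entry. Appendix C footnote h, though unclear, can be read as placing clinical assessments made before the M16-244 consent in the M16-244 case report form. If shared results are entered under the Week 0 visit date, they land on Rx Day 1 and nothing is lost. This stands as a limit: the loss depends on the feeder assessment date being kept. It does not close the gap, because neither place says which date is used or gives a mapping rule, and the SAP's windows run on dates.

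Three stronger readings are tempting and are not supported.

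- **That Week 0 is the reference for later results, so the whole efficacy course is distorted.** SAP 6.1, 10.3 and 10.4 measure change from the Study 1311.5 baseline, as do the laboratory and vital-sign sections. One phrase in Table 8 refers to a baseline in Study M16-244, but it conflicts with those sections and is a separate matter to correct.
- **That differing subjects between rows show bias.** Observed-case rows differ in composition anyway, and non-responders are discontinued under Protocol 5.4.1. Nothing in the documents links a 1–4 day gap to outcome, so no direction of bias can be claimed.
- **That 9, 18 or 36 subjects are lost.** Those are arithmetic on assumed shares. Same-day rollover is allowed and may be common.

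It is also fair to say that widening the window alone may retrieve nothing if the feeder record sits only in the Study 1311.5 data.

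**Conclusion.** The point holds in limited form. The protocol's Week 0 rule and the SAP's Week 0 window disagree for delays of 1 to 4 days. If the stand-in results keep their assessment dates, and Rx Day counts from the first M16-244 dose, they fall in no window of Tables 1–4 or 6 and drop out of the descriptive Week 0 rows.

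The damage is confined to those rows: their n, response rates, mean changes, and laboratory and vital-sign summaries. Adverse event summaries do not use these windows. Change from the Study 1311.5 baseline at later visits is unaffected under SAP 6.1. Same-day rollovers, subjects delayed more than 4 days, and any prompt rollover whose assessments were repeated on the dosing day are also unaffected. The number of subjects involved cannot be derived from the documents. The correction is worth making because it is cheap and restores valid records, not because a study conclusion turns on it.

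**What to change.** Make three linked edits to the SAP:

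1. In 6.3, state that Rx Day for the windows in Tables 1–4 and 6 counts from the first dose in Study M16-244.
2. In 6.4, state that when the delay is 4 days or less, the Study 1311.5 Week 24 record is brought into the analysis dataset as the Week 0 value.
3. In Tables 1–4 and 6, change the Week 0 row to Rx Day -4 through 1, taking the last non-missing value on or before the first M16-244 dose. This also settles which value counts if a site repeated an assessment.

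The cost is two sentences, one row in each of five tables, and a programming step to map the feeder record. Study 1311.5 data are already needed for baseline and mTSS, so no new data collection is required, and the protocol does not change.

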Appendix D. Local Requirements

Local Requirements – Japan

Section 5.3.1.1: Study Procedures

Clinical Laboratory Tests

eGFR (estimated by CKD-EPI Japan formula)

Tuberculosis Screening

All subjects will be tested for TB by either the QuantiFERON-TB Gold Test (or equivalent) or a TB Skin Test or equivalent most commonly the Purified Protein Derivative (PPD) at the Week 24. If premature discontinuation occurs prior to Week 24 visit TB testing should occur at EOS visit as specified in [Appendix C](#).

A TB Skin Test or equivalent should be utilized only when a QuantiFERON®-TB Gold Test is not possible for any reason (unless both tests are required per local guidelines).

- QuantiFERON®-TB Gold Test will be analyzed by the central laboratory (QuantiFERON test is preferred over TB Skin Test).
- If the QuantiFERON®-TB Gold Test is NOT possible (or if both the QuantiFERON®-TB Gold Test and the PPD Skin Test are required per local guidelines) the PPD Skin Test will be performed according to standard clinical practice.
- The PPD Skin Test should be read by a licensed healthcare professional between 48 and 72 hours after administration. A subject who does not return within 72 hours will need to be rescheduled for another skin test.
- The reaction will be measured in millimeters (mm) of induration and induration ≥ 5 mm is considered a positive reaction. The absence of induration will be recorded as "0 mm" not "negative."
- If PPD and/or the QuantiFERON®-TB Gold test (or IGRA equivalent) is positive, or if there is a repeat indeterminate QuantiFERON®-TB Gold test (or IGRA equivalent) upon retesting, subjects may continue in the study if further

work up (according to local practice/guidelines) establishes conclusively that the subject has no evidence of active tuberculosis.

- If the subject is diagnosed with active tuberculosis, the subject should not receive any further study drug and follow the premature treatment discontinuation procedure (Early EOT visit) in Section [5.4.1](#).
- **If presence of latent tuberculosis is established treatment should be initiated and maintained according to local country guidelines.** It is also necessary to report it as an adverse event in the source documents and eCRFs.
- If subject is known to have a positive QuantiFERON®-TB Gold or PPD test in Study 1311.5 Screening period do not repeat in this study.
- Subjects who have had an ulcerating reaction to the TB Skin Test in the past should not be re-exposed and should not be tested by a PPD skin test.

In the case of a tuberculosis-related adverse event, a supplemental case report form that provides additional information is be completed by the investigator or designee.

Section 7.0: Protocol Deviations

AbbVie does not allow intentional/prospective deviations from this protocol unless when necessary to eliminate an immediate hazard to study subjects. The principal investigator is responsible for complying with all protocol requirements, and applicable global and local laws regarding protocol deviations. If a protocol deviation occurs (or is identified) after a subject has been enrolled, the principal investigator is responsible for notifying Independent Ethics Committee (IEC)/Independent Review Board (IRB) regulatory authorities (as applicable), and the following AbbVie Clinical Monitor(s):

Primary Contact:

Alternate Contact:

Such contact must be made as soon as possible to permit a review by AbbVie to determine the impact of the deviation on the subject and/or the study.

In Japan, the Investigator will record all protocol deviations in the appropriate medical records at site.

Section 9.3.1 Informed Consent Form and Explanatory Material

Prior to the performance of any study specific procedures, including discontinuation of any protocol prohibited medications, the investigator or representative will explain the nature of study procedures and the study to the subject and if applicable per local requirements the subject's legal representative, and all questions regarding the study will be answered. The informed consent form will be reviewed and consent to participate documented by dated signature of the representative and the person administering the informed consent.

In Japan, the principal investigator will prepare the consent form and explanatory material required to obtain subject's consent to participate in the study with the cooperation of the sponsor and will revise these documents as required. The prepared or revised consent forms and explanatory material will be submitted to the sponsor. Approval of the IRB will be obtained prior to use in the study.

Section 9.3.2: Revision of the Consent Form and Explanatory Material

In Japan, when important new information related to the subject's consent becomes available, the principal investigator will revise the consent form and explanatory material based on the information without delay and will obtain the approval of the IRB prior to use in the study. The investigator will provide the information, without delay, to each subject already participating in the study, and will confirm the intention of each subject to continue the study or not. The investigator shall also provide a further explanation using the revised form and explanatory material and shall obtain written consent from each subject of their own free will to continue participating in the study.

Section 13.0: Completion of the Study

The investigator will conduct the study in compliance with this protocol and complete the study within the timeframe specified in the contract between the investigator (**Director of the Site in Japan**) and AbbVie. Continuation of this study beyond this date must be mutually agreed upon in writing by both the investigator (**Director of the Site in Japan**) and AbbVie. The investigator will provide a final report to the IEC/IRB following conclusion of the study, and will forward a copy of this report to AbbVie or their representative.

The investigator (**Director of the Site in Japan**) must retain any records related to the study according to local requirements. If the investigator (**Director of the Site in Japan**) is not able to retain the records, he/she must notify AbbVie to arrange alternative archiving options.

AbbVie will select the signatory investigator from the investigators who participate in the study. Selection criteria for this investigator will include level of participation as well as significant knowledge of the clinical research, investigational drug and study this protocol. The signatory investigator for the study will review and sign the final study report in accordance with the European Agency for the Evaluation of Medicinal Products (EMEA) Guidance on Investigator's Signature for Study Reports.

The end-of-study is defined as the date of the last subject's last visit.

Appendix C: Study Activities Table

	Treatment					Follow-Up		Follow-up Phone Call
	V1	V2	V3	V4	V5 (EOT/Early EOT)	V6	EOS (EOT/Early EOT + 16 Weeks)	
Week	0	4	12	24	36	48	52	56
Day	1 ± 4	29 ± 4	85 ± 4	169 ± 4	253 ± 4	336 ± 4	365 ± 4	365 ± 4
HBV DNA*	X			X			X	

* If subject had positive Hepatitis B Core Antibody or Hepatitis B Surface Antibody in Study 1311.5 and the reflex Hepatitis B virus DNA quantification level was undetectable at screening the HBV DNA level must be monitored at least every 6 months.

In the case of a tuberculosis-related adverse event, a supplemental case report form that provides additional information is be completed by the investigator or designee.

Local Requirements – Germany

Section 5.3.1.1 Study Procedures – X-Ray Assessments

The modified Total Sharp Score (mTSS) method, including distal interphalangeal joints, will be used to evaluate radiographic evidence of damage.¹⁹ X-rays of hands, wrists and feet. The x-rays will be performed at two time points (Weeks 24 and 48, detailed in [Appendix C](#)). Images will be read centrally for each subject in a random order and without knowledge of time point or subject identity. Subjects who prematurely discontinue from study drug will not be required to collect x-rays at each designated time point, unless they received a dose within the 16 weeks prior to the scheduled time point.

For subjects who have had an X-Ray performed within 2 weeks before the scheduled protocol X-ray assessment, no additional X-Rays should be performed.

Local Requirements – France**Section 5.2.1 Inclusion Criterion 2**

Women of childbearing potential must agree to use at least one of the following methods of contraception throughout the study including **20 weeks** after the last study drug dose is given:

- combined (estrogen and progestogen containing) hormonal birth control (oral, intravaginal, transdermal) associated with inhibition of ovulation initiated at least one month prior to study participation
- progestogen-only hormonal birth control (oral, injectable, implantable) associated with inhibition of ovulation initiated at least one month prior to study participation
- bilateral tubal occlusion/ligation
- intrauterine device (IUD)
- intrauterine hormone-releasing system (IUS)
- Vasectomized sexual partner(s) (the vasectomized partner should have received medical assessment of the surgical success and is the sole sexual partner of the trial participant).
- True abstinence: Refraining from heterosexual intercourse when this is in line with the preferred and usual lifestyle of the subject (periodic abstinence [e.g., calendar, ovulation, symptothermal, post-ovulation methods] and withdrawal are not acceptable).

Women of childbearing potential are defined as having experienced menarche and are:

- not postmenopausal (12 months with no menses without an alternative medical cause)
- not permanently sterilized (e.g., hysterectomy, bilateral oophorectomy or bilateral salpingectomy).

Section 5.2.2 Exclusion Criterion 1

1. Female subject who is pregnant, breastfeeding or is considering becoming pregnant during study participation, including **20 weeks** after the last dose of study drug is given.

Section 5.2.4 – Contraception Recommendations and Pregnancy

Female subjects of childbearing potential must be ready and able to use highly effective methods of birth control per ICH M3(R2) that result in a low failure rate of less than 1% per year when used consistently and correctly. Or subjects must have only vasectomized sexual partner(s), or be abstinent. The method chosen must be practiced throughout the study including **20 weeks** after the last dose of study drug is given.

Women of childbearing potential are defined as having experienced menarche and are:

- not postmenopausal (12 months with no menses without an alternative medical cause)
- not permanently sterilized (e.g., tubal occlusion, hysterectomy, bilateral oophorectomy or bilateral salpingectomy).

The following is a list of accepted contraception methods:

- combined (estrogen and progestogen containing) hormonal birth control (oral, intravaginal, transdermal) associated with inhibition of ovulation initiated at least 1 month prior to study participation
- progestogen-only hormonal birth control associated with inhibition of ovulation initiated at least one month prior to study participation
 - bilateral tubal occlusion/ligation
 - intrauterine device (IUD)
 - intrauterine hormone-releasing system (IUS)

- Vasectomized sexual partner(s) (the vasectomized partner should have received medical assessment of the surgical success and is the sole sexual partner of the trial participant).
- True abstinence: Refraining from heterosexual intercourse when this is in line with the preferred and usual lifestyle of the subject (periodic abstinence [e.g., calendar, ovulation, symptothermal, post-ovulation methods] and withdrawal are not acceptable).

In addition, both female subjects of childbearing potential and male subjects with female partners of childbearing potential, taking MTX as background medication, must follow the national regulatory guidelines regarding contraception while taking these medications.

See Pregnancy Testing paragraph in Section [5.3.1.1](#) for pregnancy testing instructions.

